The results of our recent LMA trial indicate that surfactant delivery via LMA produces immediate improvements in oxygenation comparable to delivery via ETT, and decreased need for subsequent ventilatory support. However, because our previous INSURE approach for ETT delivery of surfactant included morphine, a slow-onset, long acting analgesic which likely contributed to the need for invasive ventilation, it remains unclear whether LMA delivery of surfactant is as effective as our new INSURE technique, which is designed to avoid respiratory depression.

Since our last trial began, the results of a small randomized trial were published, where the 11 babies who received surfactant via LMA showed improvements in oxygenation comparable to those in our study, whereas no change occurred in the surfactant-untreated (CPAP-only) group (Attridge, Stewart, Stukenborg, & Kattwinkel, 2013). In a piglet model of RDS, surfactant administered via LMA had physiologic effects similar to those of ETT administration (Roberts et al., 2010). The only ongoing clinical trial on delivery of surfactant via LMA to human neonates with RDS (Roberts et al., NCT01116921 at www.clinicaltrials.gov) is examining the effectiveness of this procedure (versus no surfactant treatment) in decreasing the need for later mechanical ventilation.

From the foregoing, it is apparent that clinical trials are still needed to address the relative efficacy of surfactant delivered via LMA versus optimized INSURE approaches. In this proposal, we extend our investigations of surfactant delivery by LMA to the current clinical context in which premedication for INSURE comprises atropine and remifentanil.

Hypothesis:

Surfactant therapy delivered via LMA is not inferior to surfactant therapy delivered via transient intubation (INSURE technique) with short-acting narcotic premedication for mild to moderate RDS in preterm neonates.

Aims:

1. To compare the rate of failure of surfactant therapy delivered via LMA to the rate of failure of surfactant therapy delivered via transient intubation (INSURE technique) in avoiding mechanical ventilation in neonates 27 to 36 weeks' gestation with mild to moderate RDS.

1a. To evaluate the success of remifentanil as premedication for transient intubation (INSURE technique) as compared to morphine used in our previous trial.

2. To further evaluate the safety of surfactant administration via LMA.

B. Study Design/C. Subject Population

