Although the study interventions are limited to the airway used for surfactant administration in the first 1 to 3 days of life, and clinical management or follow-up are not otherwise conditioned by the study, all subjects enrolled will continue in the study up to discharge from AMC, for the purposes of data collection. This will include:

- the FiO₂ and mode of respiratory support before enrollment and at 0, 1, 12, 24, and 48 hours, and 7 and 28 days after initial surfactant administration,
- any need for additional doses of surfactant,
- any need for intubation, and
- any need for mechanical ventilation.

D. Data Analysis

A copy of the data collection sheet that will be used for the study is included.

Primary Outcome Measures: The primary outcome will be success of the surfactant administration strategy in avoiding mechanical ventilation in the first 120 hours of life.

Secondary Outcome Measures:

- Number of surfactant doses
- Days on assisted ventilation
- Day on any noninvasive respiratory support (CPAP/NIPPV modes)
- Days until off respiratory support (supplemental oxygen and/or pressure support)
- Rate pneumothorax and/or pneumomediastinum
- Rate of BPD as defined by oxygen dependence at later of 28 days or 36 weeks' postmenstrual age
- Complications during insertion of LMA or ETT
- Mortality rate

Planned post-hoc analyses include timing of failure by treatment group, which should illuminate the mechanisms of failure by treatment strategy.

➤ Baseline comparability:

Baseline differences between ETT group and LMA group will be compared using t-tests for continuous variables (birth weight, gestational age, age and FiO₂ at enrollment) and chi-square test for categorical variables (race, sex, prenatal care, antenatal steroids, mode of delivery, multiple gestation)

➤ Primary outcome measure:

Our primary outcome for the study is the proportion of infants that will reach the early and/or late failure criteria. The incidence of the failure criteria will be compared using chi-square statistics.

➤ Sample size/Power analysis:

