The sample size was estimated based on results from the recent study on this population, at the Albany Medical Center NICU. We will thus expect that 30% of the LMA group will meet failure criteria, i.e., the LMA success rate in avoiding later intubation and ventilation will be 70%. For a non-inferiority design, with a clinically relevant non-inferiority margin of 20%, a sample of 130 patients (65 per group) will be needed to conclude non-inferiority of the LMA method compared to INSURE (calculated using a one-sided $\alpha=0.05$, β error=0.20).

➤ Secondary outcome measures:

Groups will be analyzed for secondary outcome differences using chi-square statistics for categorical data, and t-test or non-parametric tests for continuous data, as appropriate for the distribution obtained. The FiO_2 response to surfactant treatment strategies will be compared from baseline to 1 and 8 hours using repeated measures ANOVA and post-hoc Dunnett's test. Time to wean off respiratory support will be compared between groups using Kaplan-Meier analysis, with censoring at discharge.

➤ Interim Analyses:

Reports for the IRB will be prepared after one year of initiation of the trial or enrollment of 50 patients, whichever comes first. Data on the primary outcome, mortality, and major adverse events on the first 50 patients, will be submitted to [name] for purposes of safety monitoring. A difference in primary outcome at the $p<0.01$ level, or a consistent trend towards differences in major adverse events will constitute criteria for recommending that the study be stopped.

E. Risks

- Risk category: Greater than minimal.

This study is considered as a greater than minimal risk study. The study design includes a decreased use of laryngoscopy for tracheal intubation, which is currently the standard method of surfactant delivery. Laryngoscopy is associated with apnea, minor abnormalities in cardiac rhythm, obstructed respiration, increase in systolic blood pressure, decreased heart rate and transcutaneous oxygen tension in preterm neonates during the laryngoscopy (Carbajal, 2007)

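### The trial is framed and sized for non-inferiority with a 20-point margin, but the stated primary analysis is a chi-square comparison that never uses the margin

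*Combined protocol and SAP*

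**What the plan says.** The Hypothesis, just before the Aims, states: "Surfactant therapy delivered via LMA is not inferior to surfactant therapy delivered via transient intubation (INSURE technique") with short-acting narcotic premedication.

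Section D, Sample size/Power analysis, is written for that hypothesis: "For a non-inferiority design, with a clinically relevant non-inferiority margin of 20" percent, one-sided alpha 0.05, beta 0.20, 65 per group and 130 in total. The one failure rate supplied is for LMA: "We will thus expect that 30% of the LMA group will meet failure criteria". No INSURE rate is given.

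Section D, Primary outcome measure, contains two sentences. The first defines the endpoint: "Our primary outcome for the study is the proportion of infants that will reach the early and/or late failure criteria". The second is the entire analysis: "The incidence of the failure criteria will be compared using chi-square statistics".

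Elsewhere in section D the same test is used for ordinary comparisons. Baseline categorical variables are compared by chi-square, and for secondary outcomes the text is "Groups will be analyzed for secondary outcome differences using chi-square statistics for categorical data". The interim stopping criterion begins "A difference in primary outcome at the" p<0.01 level.

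**The concern.** A chi-square comparison of two proportions, without further specification, tests whether they are equal. A non-inferiority claim needs a different null hypothesis, namely that LMA failure exceeds INSURE failure by 20 points or more, and evidence against it. The plan provides the margin for planning but does not carry it into the analysis.

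Two things follow. First, neither outcome of the planned test answers the question: a significant result shows that the rates differ, and a non-significant result shows only that a difference was not demonstrated. Second, without a decision rule, a non-significant result could be taken as support for LMA. In a trial of this size that would happen often even when LMA is worse by the full margin.

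**Working it through.** **Inputs from the protocol.** 65 per group; margin 20 points; one-sided alpha 0.05; power 80%; LMA failure 30%.

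**Assumptions, because the protocol is silent.** The INSURE failure rate is taken as 30%, with a range of 20% to 40%. The chi-square level is taken three ways: one-sided 0.05, two-sided 0.05, and two-sided 0.05 with continuity correction.

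**1. The plan's sample size belongs to a margin-based test.** With 30% failure in both arms,

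n per group = (1.645 + 0.842)² × (0.3×0.7 + 0.3×0.7) / 0.20² = 6.185 × 0.42 / 0.04 = 64.9, rounded up to 65.

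This matches the stated figure. It also shows that the margin is in absolute points: read as 20% of 70% (14 points), it would need about 133 per group. A two-sided chi-square test to detect 30% against 50% would need 93 per group. The 65 therefore comes from a comparison with the margin, not from a test of equality.

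**2. How the two procedures behave with 65 per group.** The probabilities come from exact enumeration of two independent binomial outcomes. The margin-based test is the Farrington-Manning score test at a difference of 0.20, critical value 1.645.

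| True failure, LMA / INSURE | Chi-square non-significant: one-sided / two-sided / corrected | Score test concludes non-inferiority |
|---|---|---|
| 50% / 30% (at the margin) | 25% / 34% / 42% | 5.1% |
| 40% / 20% (at the margin) | 19% / 28% / 36% | 5.1% |
| 60% / 40% (at the margin) | 26% / 39% / 46% | 4.6% |
| 30% / 30% (planning case) | not needed here | 80.9% |

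In the first three rows LMA is worse by exactly the margin, so any claim of non-inferiority is false. Across INSURE rates of 20% to 40% the score test's false-claim rate stays between 4.6% and 5.4%. Reading chi-square non-significance as non-inferiority gives 19% to 46%. In the planning case the two-sided uncorrected chi-square is significant about 5% of the time, so the planned 80% power cannot refer to it.

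**3. An example.** Suppose 28/65 (43.1%) fail on LMA and 20/65 (30.8%) on INSURE, a difference of 12.3 points.

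- Chi-square: pooled proportion 48/130 = 0.369; standard error √(0.369 × 0.631 × 2/65) = 0.0847; z = 0.123/0.0847 = 1.45. So p = 0.073 one-sided, 0.146 two-sided and 0.203 continuity-corrected. None is significant at 0.05.
- Margin: the 90% score interval for LMA minus INSURE is −1.6 to 25.8 points. The upper limit exceeds 20, so non-inferiority is not shown.

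The same data thus give no significant difference and no demonstration of non-inferiority. With 20/65 INSURE failures, non-inferiority would require at most 24/65 on LMA.

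**The case against.** The strongest reply is that the protocol is short and the pieces are all there. The hypothesis gives the direction, and the sample-size paragraph, directly below the primary analysis, gives the margin, alpha and sidedness. A reader could reconstruct the intended test. Chi-square statistics is also a loose term, and the square of a margin-based score statistic is itself referred to a chi-square distribution. On this view the sentence is careless drafting.

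That may explain the sentence, but it does not supply a rule. The same term is used for baseline and secondary differences, and nothing marks the primary use as different. Even on the generous reading, the interval method, the confidence level and the criterion for the claim are left open. The level matters: with a two-sided 95% interval, power at 65 per group falls from about 80% to about 70%.

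Three narrower points stand:

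- The plan does have a margin; what is missing is its use in the analysis.
- The 19% to 46% figures describe a possible misreading, not a rule the protocol states.
- The interim criterion serves safety monitoring and is weak evidence about the final analysis.

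A score interval is also not the only sound choice. A Wald interval with the same rule has exact power of 80.6% when failure is 30% in both arms, and a false-claim rate of 4.6% at 50% against 30%.

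**Conclusion.** The concern holds and should be fixed before the analysis. The stated primary test does not address the stated hypothesis, the stated power belongs to a different test, and no criterion for concluding non-inferiority appears in the document. This conclusion comes from the text alone and needs no assumed rates.

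The size of the possible harm does rest on assumptions: the INSURE failure rate, the chi-square level, and a reader treating non-significance as non-inferiority. Under those, the false-claim rate at the margin is about four to nine times the planned 5% (19/5 = 3.8 to 46/5 = 9.2). The sample size itself is not in dispute here; it reproduces when failure is 30% in both arms.

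**What to change.** In section D, Primary outcome measure, replace the chi-square sentence with wording such as:

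*The primary analysis is the difference in failure proportion (LMA minus INSURE) with a score confidence interval. Non-inferiority is concluded if the upper limit of the two-sided 90% confidence interval (one-sided 95%, matching the sample size) is below 20 percentage points.*

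A chi-square test of difference may be kept as supplementary, with a statement that it is not evidence of non-inferiority.

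The sentence uses the failure composite named in that paragraph. Section D first describes the primary outcome as avoidance of mechanical ventilation in the first 120 hours of life, so the sponsor should confirm which endpoint the rule applies to.

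The cost is wording only. The data are the same, and 130 patients still give about 81% power if failure is 30% in both arms.

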Reporting period: AEs will be recorded from the time of informed consent until 72 hours following the last use of the LMA or ETT for non-serious AEs, and until 30 days after the last use of the LMA or ETT for serious AEs. Any AE that occurs between the time informed consent is obtained and the initial airway insertion, that is considered related to a protocol-specified procedure, must be reported.

Procedures for assessing, recording and reporting AEs: Throughout the duration of the study, the investigators will closely monitor each subject for clinical evidence of device-related events, and monitor all clinically information for evidence of AEs. AEs not explained by the infant's underlying illness which occur during the course of the study will be reported in detail on the appropriate forms to the IRB, and followed until resolved or stable. All serious AEs will be reported to the IRB within 24 hours.

Grading of AEs:

- Mild - sign or symptom noticeable, but easily tolerated by the patient, and not expected to have a clinically significant effect on the baby's overall health and well-being. Not likely to require specific medical attention.

- Moderate - causes interference with usual function or affects clinical status. May require medical intervention.

- Serious - incapacitating or significantly affecting clinical status. Likely requires medical intervention and/or close follow-up.

Expected adverse events (AEs):

The following AEs associated with prematurity, the clinical course of RDS, or treatments for these conditions, are expected with the approximate frequencies listed in the Table. These AEs are actually or may be potentially relevant to the LMA study protocol.

Adverse events	Expected %
During surfactant administration procedure	
Desaturation > 1 min	5% to 20%
Airway obstruction	39%
Bradycardia	34%
Surfactant reflux onto CO ₂ detector	5%
Re-intubation	5%
LMA replacement	5 to 10%
Others (observer, specify):	
Clinical complications of prematurity and RDS	
Pneumothorax	6 to 17%
Other pulmonary air leak	15%
Pulmonary hemorrhage	1 to 7%
Hypotension	15%
Oliguria	10%
Intraventricular hemorrhage (grade \geq 2)	0.5% to 10%
Relevant Outcomes	
Chronic lung disease	5% to 15%
Mortality (depends on gestational age)	1% to 5%

Serious adverse events (SAE):

A SAE is defined as an adverse effect that meets any of the following serious outcomes:

- o Is fatal;
- o Is life-threatening;
- o Results in persistent or significant disability;

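### For mortality and other rare harms, the planned chi-square tests have little power at 65 per group, so Aim 2 should rest on risk differences with intervals and not on non-significance

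*Combined protocol and SAP*

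**What the plan says.** The second aim is "To further evaluate the safety of surfactant administration via LMA" (Aims). It carries no hypothesis, margin or rule for reaching a conclusion.

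The secondary outcomes in Section D that bear on safety are "Mortality rate", pneumothorax and/or pneumomediastinum, BPD, and complications while the LMA or ETT is being inserted. Their final analysis is one line under Secondary outcome measures: "Groups will be analyzed for secondary outcome differences using chi-square statistics for categorical data". That paragraph states no significance level, effect estimate or confidence interval.

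The sample size belongs to the primary outcome alone: "a sample of 130 patients (65 per group) will be needed to conclude non-inferiority of the LMA method compared to INSURE". The 20-point margin, one-sided 5% level and 80% power are stated for that comparison only.

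The expected adverse events table in Section E gives the event rates. The row "Mortality (depends on gestational age") shows 1% to 5%. Pneumothorax is 6% to 17%, chronic lung disease 5% to 15%, bradycardia during the procedure 34% and airway obstruction during the procedure 39%.

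The plan also provides for recording and grading of adverse events, reporting of serious events to the IRB within 24 hours, and a safety report covering the first 50 patients.

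**The concern.** A test for a difference answers whether the data contradict equality. When few events are expected, a non-significant result is likely whether or not the LMA adds risk, so it says little about safety. The trial is built to show non-inferiority on treatment failure, and readers of such a trial easily take p>0.05 on deaths or air leak as a second finding of no harm. Section E already describes pneumothorax in the group's previous trial as alike in the two arms, without an interval.

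At stake is what the report may say under Aim 2. The planned p-value does not show how large an excess of deaths, air leak or BPD the data leave open.

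**Working it through.** **Inputs.** 65 per group (Section D, Sample size/Power analysis) and the expected rates in the Section E table. Three assumptions are mine:
- Secondary tests are two-sided at 5%, since no level is stated.
- The chronic lung disease row stands for BPD.
- The pneumothorax row stands for the air-leak outcome. That outcome also counts pneumomediastinum, so its rate, and hence its power, may be somewhat higher.

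**Step 1: the plan's own figure.** The plan says "We will thus expect that 30% of the LMA group will meet failure criteria". Taking 30% failure in both groups and a 20-point margin:

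n per group = (1.645 + 0.842)² × 2 × 0.30 × 0.70 / 0.20² = 64.9, rounded up to 65.

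The stated 130 is reproduced.

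**Step 2: power of the planned test.** With a events in one group and b in the other, 65 in each, Pearson's statistic reduces to

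X² = 130(a − b)² / [(a + b)(130 − a − b)], significant above 3.84.

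Power is the sum, over all pairs (a, b) with X² > 3.84, of Bin(a; 65, p₁) × Bin(b; 65, p₂). For a doubling of risk in the LMA group:

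| Outcome | Rates | Expected events per group | Power, chi-square | n per group for 80% power |
|---|---|---|---|---|
| Mortality | 1% to 2% | 0.65 and 1.3 | 2% | 2319 |
| Mortality | 3% to 6% | 1.95 and 3.9 | 12% | 749 |
| Mortality | 5% to 10% | 3.25 and 6.5 | 19% | 435 |
| BPD | 5% to 10% | 3.25 and 6.5 | 19% | 435 |
| BPD | 15% to 30% | 9.75 and 19.5 | 54% | 121 |
| Pneumothorax | 6% to 12% | 3.9 and 7.8 | 22% | 356 |
| Pneumothorax | 17% to 34% | 11.05 and 22.1 | 62% | 103 |
| Bradycardia | 34% to 68% | 22.1 and 44.2 | 97.5% | 33 |
| Airway obstruction | 39% to 78% | 25.35 and 50.7 | 99.7% | 24 |

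For mortality, the chance of missing a doubling is 100 − 19 = 81% at the top of the expected range and 100 − 2 = 98% at the bottom.

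**Step 3: the same in counts.** With 3 INSURE deaths:
- 9 LMA deaths give X² = 130 × 36 / (12 × 118) = 3.31, p = 0.07.
- 10 LMA deaths give X² = 130 × 49 / (13 × 117) = 4.19, which is significant.

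A tripling in the observed counts would therefore still be reported as non-significant.

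**Step 4: sensitivity.**
- The chi-square test is not anti-conservative for mortality: its exact type I error is 0.4% at a common rate of 1% and 4.7% at 5%.
- Fisher's exact test would lower power for a mortality doubling to 0.1% (1% to 2%) and 10% (5% to 10%), so an exact test alone does not help.
- A one-sided 5% level gives about 12% and 29% for the same two cases (normal approximation).

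**Step 5: what an interval would show.** Newcombe's 95% interval combines the Wilson limits (l, u) of each group. For the difference d = p₁ − p₂, with group 1 the LMA, the upper limit is d + √[(u₁ − p₁)² + (p₂ − l₂)²]. With 0 of 65 in each group, the Wilson upper limit is 3.84 / (65 + 3.84) = 5.6%, so the interval is ±5.6 points. Further cases:

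| LMA vs INSURE events | Difference, points | 95% interval, points |
|---|---|---|
| 2 vs 2 | 0 | −7.8 to +7.8 |
| 3 vs 3 | 0 | −8.6 to +8.6 |
| 6 vs 3 (X² = 1.07, p = 0.30) | +4.6 | −4.9 to +14.6 |
| 11 vs 11 | 0 | −13.1 to +13.1 |

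**The case against.** Four objections deserve an answer.

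**Not all safety outcomes are rare.** This stands. Power for a doubling exceeds one half for BPD at 15% and pneumothorax at 17%. Procedural events at 34-39% would show a doubling almost surely; for these, 80% power is reached at rates of about 59% and 64%, a rise of about 25 points. A reader might infer that non-significance is near-certain on every safety outcome whatever the truth. The table contradicts that.

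**Aim 2 is modest and has other support.** This stands in part. The aim is only to evaluate safety further, and nothing ties it to the chi-square tests alone. Adverse event recording and the interim report, whose adverse-event criterion is a trend and not a significance test, both remain. A reader might infer that the plan can support no safety statement at all; the documents do not bear that out. These provisions are monitoring and description, however, and give no end-of-trial comparison with a measure of precision.

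**The plan nowhere says that p>0.05 will be reported as safety.** That is correct, and it should not be read into the plan. But the plan also gives no other way to read a null result.

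**Intervals would be wide, and readers could compute them from posted counts.** They would be wide, as in almost any trial of 130 infants. Showing that width is the purpose, and leaving the calculation to readers does not settle how the sponsor words its own conclusion.

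**Conclusion.** The point holds for mortality and for the low end of the expected air-leak and BPD rates. On these outcomes, at 65 per group, non-significance would be the usual result even if the LMA doubled the risk, and it cannot support a claim of equal or acceptable risk. For mortality a doubling goes undetected with a probability of 81% to 98%, which is high but not certainty.

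The size of the problem rests on the Section E rates, full enrolment of 65 per group and the assumed two-sided 5% level. A one-sided 5% level does not change the conclusion.

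The primary comparison and the sample size are unaffected. This is a cheap improvement to the analysis and reporting of Aim 2.

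**What to change.** In Section D, Secondary outcome measures, add for mortality, pneumothorax/pneumomediastinum, BPD and insertion complications:

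- The main summary is the number of events in each group and the risk difference, LMA minus INSURE, with a 95% score-type interval (Newcombe or Miettinen-Nurminen), in place of the chi-square test alone.
- The Aim 2 conclusion is worded by the excess harm that each interval does and does not exclude.
- A p-value above 0.05 is not reported as evidence of equal safety.

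The cost is a few sentences in the analysis plan, with no further patients, data collection or change to the primary analysis. The downside is a more cautious safety statement, because the intervals for deaths will be wide whatever the counts turn out to be.

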- Multi-center, randomized controlled trial. The participating centers are Albany Medical Center, Bellevue Woman's Center at Ellis Hospital, and Golisano Children's Hospital. Each center will obtain approval from that center's own Institutional Review Board. It is anticipated that the study will take 2 years to complete.

[figure not shown]
Patient Enrollment:

- The investigators and/or study coordinator will evaluate all infants admitted to the NICU who are less than 48 hours of life from 27 through 36 completed weeks' gestation with mild-moderate RDS.
- If they meet the pre-defined inclusion criteria and informed consent is obtained, they will be randomized to either the INSURE group or LMA group for the initial surfactant administration. Patients will be block randomized in one of three gestational age groups: 27 0/7 - 28 6/7 weeks, 29 0/7 - 32 6/7 weeks, 33 0/7 - 36 6/7 weeks.
- Randomization process: An anticipated 130 patients will be enrolled in the study. Patients will be randomized into three groups using a blind randomization selection method. After computer-generated block randomization, the 130 numbered cards will be placed in sealed, numbered envelopes, and kept in a NICU nurse practitioner office. Each card will indicate LMA or INSURE group and include an identifier code number. After obtaining the signed consent form, the investigators or coordinator will open the next envelope in the appropriate gestational age block.
- Inclusion Criteria:
 - Gestational age (GA) 27 0/7 weeks to 36 6/7 weeks
 - Age < 48 hours
 - Mild-moderate RDS as defined by an FiO₂ requirement of 0.30 - 0.60 on either CPAP or nasal intermittent positive pressure ventilation (NIPPV) for at least two hours to maintain SpO₂ 90-95%
 - Written consent obtained
- Exclusion Criteria:
 - Prior tracheal intubation

- Prior surfactant therapy
- Evidence of pneumothorax, pneumomediastinum, or pneumopericardium
- $\text{FiO}_2 > 0.60$
- Craniofacial or other airway malformation
- Major congenital malformation (cardiac and thoracic defects)
- Apgar score of ≤ 3 at 5 minutes of life or evidence of encephalopathy
- Weight less than 800 grams

Study/Intervention:

The diagram below is a graphic depiction of the study protocol. Criteria for assisted ventilation and other respiratory support will be the same for both groups.

• **INSURE (control group): Atropine + remifentanil + intubation (ETT) + Infasurf**

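### Minor, secondary analysis: FiO2 response is to be compared at 1 and 8 hours, but the listed FiO2 collection times contain no 8-hour reading, and the LMA-versus-INSURE contrast is not specified

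*Combined protocol and SAP*

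**What the plan says.** Section D, Secondary outcome measures, opens with comparisons between the arms: "Groups will be analyzed for secondary outcome differences using chi-square statistics for categorical data", with t-tests or non-parametric tests for continuous data. It then says that the FiO2 "response to surfactant treatment strategies will be compared from baseline to 1 and 8 hours using repeated measures ANOVA", with Dunnett's test as the post-hoc step. It does not say which contrasts that test covers.

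The collection schedule stands at the end of the study procedures, just before section D. It is introduced by "all subjects enrolled will continue in the study up to discharge from AMC, for the purposes of data collection. This will include", and its first item covers FiO2 together with the "mode of respiratory support before enrollment and at 0, 1, 12, 24, and 48 hours, and 7 and 28 days after initial surfactant administration".

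Section D also says: "A copy of the data collection sheet that will be used for the study is included". That sheet is not in the text available for review.

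On design, Patient Enrollment says: "Patients will be block randomized in one of three gestational age groups". There are two arms, LMA and INSURE. FiO2 at enrollment is among the variables named under Baseline comparability.

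**The concern.** The analysis names a time that the schedule does not. If the sites collect what is listed and no more, the 1-hour comparison can be made and the 8-hour comparison has no data specified for it. Someone would then have to choose a replacement time, possibly after seeing results.

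The second issue is what the named methods deliver. The aim is a difference between arms. Dunnett's test compares several means with one reference, and the natural reference here is baseline. That shows whether FiO2 fell after treatment, not whether it fell equally under LMA and INSURE. The background relies on the finding that "surfactant delivery via LMA produces immediate improvements in oxygenation comparable to delivery via ETT", so the between-arm estimate is the useful one.

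The stakes are limited. FiO2 response is not among the eight listed secondary outcomes, and nothing in the primary comparison depends on it.

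**Working it through.** **The plan's own figure.** The FiO2 analysis has no stated figure. The only design calculation is the sample size. With 70% success assumed in both arms, a margin of 20 points, one-sided alpha 0.05 and power 80%, n per arm = 2 × 0.70 × 0.30 × (1.645 + 0.842)² / 0.20² = 64.9, so 65 per arm and 130 in total. This reproduces the plan's number and does not bear on the FiO2 question.

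**Time points.**
- Needed after baseline (Secondary outcome measures): 1 h and 8 h.
- Listed (collection schedule): before enrollment, then 0, 1, 12, 24 and 48 h, and 7 and 28 days. That is 1 + 7 = 8 points.
- Needed but not listed: 8 h, which is one of two.
- Distance to the nearest listed readings: 8 − 1 = 7 h back and 12 − 8 = 4 h forward.

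Elsewhere, 8 hours appears only in Failures and Re-dosing of surfactant, as a cut-off for a second dose and not as a time for reading FiO2.

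**What a reading at 8 or 12 hours would reflect.** Under those headings, a second dose inside 8 hours counts as a late failure and goes by ETT in both arms. A single second dose after 8 hours is not in itself a failure and goes by LMA in the LMA arm. An 8-hour reading may thus follow an early second dose, and a 12-hour reading may follow an early or a later one. Neither is purely a response to the first dose, and the two do not measure the same thing.

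**Dunnett's test.**
- Between arms: with two arms there is one comparison and nothing to adjust. On simulated data with 65 per arm, Dunnett's test and the two-sample t-test both gave p = 0.0702.
- Against baseline: there are two comparisons with a shared reference, and the adjustment does act. The large-sample two-sided 5% critical value is 2.21 (assuming correlation 0.5 between the contrasts), against 1.96 for one comparison. This is a valid use, but it describes change over time.

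**Precision of the between-arm estimate at one time.** Let r be the correlation between baseline and follow-up FiO2, and k the baseline SD divided by the follow-up SD. Neither is in the documents; all values below are assumptions.

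Variance(change score) / variance(ANCOVA) = (k² + 1 − 2rk) / (1 − r²) = 1 + (k − r)² / (1 − r²)

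The second form cannot fall below 1. The square root is the ratio of interval widths.

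| k | r = 0.3 | r = 0.5 | r = 0.7 |
|---|---|---|---|
| 0.5 | 1.044 (width ×1.02) | 1.000 (×1.00) | 1.078 (×1.04) |
| 1.0 | 1.538 (×1.24) | 1.333 (×1.155) | 1.176 (×1.085) |
| 1.5 | 2.582 (×1.61) | 2.333 (×1.53) | 2.255 (×1.50) |

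Simulating 8,000 trials with 65 per arm, k = 1, and adjustment for baseline and three strata gave standard-error ratios of about 1.22, 1.14 and 1.07 for r = 0.3, 0.5 and 0.7. These are close to the large-sample values. No stratum effect was simulated, so this shows nothing about the gain from adjusting for strata.

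**The case against.** **The list may not be complete.** Its lead-in says what data collection will include, and the sheet may carry an 8-hour field. FiO2 around that time is also clinically relevant, because re-dosing and late failure turn on it. This stands as a limit: a reader might infer that the 8-hour comparison cannot be run, and the documents do not support that. It does not remove the mismatch. Even with an 8-hour field on the sheet, the list would need correcting.

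**Dunnett's test may be exactly what was meant.** The wording about baseline to 1 and 8 hours fits a comparison of each time with baseline, and repeated measures ANOVA can test arm-by-time. Both points stand. It would be wrong to call the test an error; what is missing is a statement of its contrasts and of the between-arm estimate to be reported.

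**The precision figures are not a property of this trial.** This also stands. The plan does not name a change score, r and k are assumed, and the range runs from no gain to about 61%.

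**Change from baseline might be suspected of being a selection artefact**, since entry depends on an FiO2 "requirement of 0.30 - 0.60 on either CPAP or nasal intermittent positive pressure ventilation". The same criterion requires that level for at least two hours, which weakens the argument, and the randomized difference is not affected by it.

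**Twelve hours might be thought contaminated by re-dosing while 8 hours is clean.** The re-dosing rules do not support this, since a second dose can precede either reading. Nor does the plan propose using 12 hours in place of 8.

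**Conclusion.** The point holds as a minor one. One of the two post-baseline FiO2 analysis times has no source in the listed schedule, and the plan does not state how the LMA-minus-INSURE difference will be estimated. The first part rests only on comparing two places in the plan and is subject to what the data collection sheet contains. The second is a gap in specification, not a wrong method. The 1-hour comparison, which bears most directly on immediate oxygenation, is covered by the schedule. The primary outcome and the 130-patient sample size are unaffected. The gain from baseline adjustment cannot be sized from the documents; the firm statement is that, in large samples, it is never less precise than a change-score contrast.

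**What to change.** 1. Before data are collected, check the data collection sheet and make the list and the analysis agree. Either add an 8-hour FiO2 to the list, or name in advance one of the listed times for the analysis. Do not substitute 12 hours for 8 without saying so.
2. State in the plan that a second surfactant dose may precede either an 8-hour or a 12-hour reading, and how such readings will be treated in the analysis.
3. Keep Dunnett's test, if wanted, as a description of 1 and 8 hours against baseline, and say that this is its role.
4. For the comparison of arms, report the LMA-minus-INSURE difference in FiO2 with a confidence interval at each time, from an ANCOVA or a mixed model adjusted for enrollment FiO2 and the three gestational-age strata used in randomization.

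The cost is one data field, or a check of the existing sheet, and a few sentences of analysis text. The adjustment variables are already collected. The primary outcome, sample size and treatment procedures do not change.
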